3.1.3 Post-Consolidation Phase and Expansion Phase

The post-consolidation cohort of 30 patients is designed to further assess the safety and efficacy of idasanutlin given as a single agent to idasanutlin treatment-naïve patients in a maintenance setting. Patients will start maintenance right after consolidation completion.

The expansion phase is designed to further assess the safety and efficacy of idasanutlin in combination with cytarabine and daunorubicin at its RP2D in induction and in combination with cytarabine in consolidation followed by a single-agent maintenance.

The expansion phase (approximately 40 patients) is composed of two cohorts: 20 patients with favorable or intermediate risk and 20 patients with high risk (see [Table 3](#)).

All expansion patients will be enrolled and treated as described in [Table 4](#), and patients in the post-consolidation cohort will receive maintenance treatment as described in [Table 5](#).

In the expansion cohorts, patients who achieve remission after up to 2 induction cycles will receive chemotherapy consolidation treatment up to 4 cycles with 1.5 mg/m² cytarabine or allo-HSCT (as per site guidelines). Patients who achieved a confirmed remission at the end of chemotherapy consolidation or allo-HSCT or who underwent allo-HSCT in MLFS after induction will receive maintenance treatment for 12 cycles (see [Table 4](#)).

Patients receiving chemotherapy consolidation in the expansion should start maintenance right after consolidation completion. Patients receiving allo-HSCT consolidation should start within 90 days of the transplant and a full pre-transplant hematologic response assessment must be provided if the transplant is performed more than 4 weeks after end of induction.

On the basis of safety, tolerability, and clinical benefit and after consultation with the Medical Monitor, patients may be allowed to continue maintenance past 12 cycles.

Table 3 Post-Consolidation and Expansion Cohorts

| Cohorts | Population |
|---|---|
| Post-consolidation | Idasanutlin treatment-naïve patients in remission who received chemotherapy consolidation but were MRD positive after induction as locally assessed |
| Expansion: favorable or intermediate risk | Favorable and intermediate risk patients (ELN 2017; see Appendix 8) |
| Expansion: high risk | Adverse-risk patients (ELN 2017; see Appendix 8) and secondary AML defined as AML evolving from AHD |

AHD=antecedent hematologic disorder; AML=acute myeloid leukemia; ELN=European Leukemia Net; MRD=minimum residual disease.

Table 4 Treatment for Expansion Phase (Favorable/Intermediate-Risk and High-Risk Cohorts)

| Cycles | Dosing Regimens |
|---|--|
| Induction Cycles 1–2 ^a | 
 • Cytarabine 200 mg/m² IV on Days 1–7 • Daunorubicin 60 mg/m² IV on Days 1–3 • Idasanutlin RP2D QD orally on Days 1–5 |
| Chemotherapy consolidation or allo-HSCT (per investigator discretion): | |
| Chemotherapy Cycles 1–4 | 
 • Cytarabine 1.5 g/m² IV on Days 1–5 over 3 hr • Idasanutlin TBD ^b QD orally on Days 1–5 |
| Allo-HSCT | As per local guidelines |
| Maintenance Cycles 1–12 ^c | 
 • Idasanutlin 150 mg QD orally on Days 1–5 ^d |

HSCT=hematopoietic stem cell transplant; QD=once a day; RP2D=recommended Phase II dose; TBD=to be determined.

^a Cytarabine/daunorubicin doses/regimen can be lowered in the second cycle as per site guidelines.

^b Dose in consolidation will be determined by the Sponsor after review of all available data. It will not exceed induction dose.

^c Based on safety, tolerability, and clinical benefit, and after consultation with the Medical Monitor, patients may be allowed to continue maintenance at the same dose past 12 cycles.

^d Based on safety, tolerability, and clinical benefit, and after consultation with the Medical Monitor, intra-patient escalation may be allowed to 200 mg.

Table 5 Treatment for Post-Consolidation Phase

| Cycle | Dosing Regimen |
|---|---|
| Maintenance Cycles 1–12 ^a | 
 • Idasanutlin 150 mg QD orally on Days 1–5 ^b |

QD=once a day.

^a Based on safety, tolerability, and clinical benefit and after consultation with the Medical Monitor, patients may be allowed to continue maintenance at the same dose past 12 cycles.

^b Based on safety, tolerability, and clinical benefit and after consultation with the Medical Monitor, intra-patient escalation may be allowed to 200 mg.

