The end of this study is defined as the date when the last patient, last visit occurs. Patients will be followed up to 2 years after last patient is enrolled or all patients have died, whichever occurs first.

Length of Study

The total length of the study, from screening of the first patient to the end of the study, is expected to be approximately 6 years.

Investigational Medicinal Products

Test Product (Investigational Drug)

Idasanutlin: Patients will self-administer idasanutlin tablets by mouth each day in the morning according to the schedule of activities.

On days when idasanutlin is given in combination with chemotherapy, idasanutlin should be administered first. During consolidation when idasanutlin is given in combination with cytarabine, idasanutlin should be administered first.

Cytarabine: Cytarabine will be administered in the first cycle of induction at a dose of 200 mg/m² daily by IV for 7 days, immediately after the corresponding dose of idasanutlin.

Dose and regimen can be lowered per investigator choice in the second induction cycle

Cytarabine will be administered in consolidation at a dose of 1.5 g/m² once a day (QD) for 5 days as an IV infusion over a minimum of 3 hours, immediately after corresponding dose of idasanutlin.

The dose of cytarabine should be calculated based on a body weight measurement within 2 days of the first day of each cycle.

Daunorubicin: Daunorubicin will be administered in induction at a dose of 60 mg/m² QD for 3 days as IV infusion, immediately after the corresponding dose of idasanutlin. Dose and regimen can be lowered per investigator choice in the second induction cycle.

The dose of daunorubicin should be calculated based on a body weight measurement within 2 days of the first day of each cycle.

Statistical Methods

Primary Analysis

The primary efficacy analysis will be the estimation of the proportion of patients with a CR at the end of induction treatment.

Determination of Sample Size

Dose finding will be conducted during the dose-escalation phase of this study. The estimated sample size follows from the dose-escalation rules for a modified continuous reassessment method (mCRM) algorithm. It is anticipated that enrollment of up to five cohorts of 3–6 patients each, for a total of 9–15 evaluable patients, will be required to establish the RP2D during the dose-escalation phase. Assuming 5 not-evaluable patients; the expected maximum sample size will be approximately 20 patients.

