Table 1 Treatment during the Dose-Escalation Phase

| Cycles | Drug Regimens |
|---|--|
| Induction Up to 2 cycles ^a | 
 • Cytarabine 200 mg/m² IV on Days 1–7 • Daunorubicin 60 mg/m² IV on Days 1–3 • Idasanutlin TBD QD (starting dose 200 mg) orally on Days 1–5 |
| Chemotherapy consolidation or allo-HSCT (per investigator discretion): | |
| Chemotherapy Up to 4 cycles | 
 • Cytarabine 1.5 g/m² IV on Days 1–5 administered over 3 hours • Idasanutlin TBD ^b QD orally on Days 1–5 |
| Allo-HSCT | 
 • As per local guidelines |
| Maintenance Cycles 1–12 ^c | 
 • Idasanutlin 150 mg QD orally on Days 1–5 ^d |

allo-HSCT = allogenic hematopoietic stem cell transplant; QD=once a day; TBD=to be determined.

^a Cytarabine/daunorubicin doses/regimen can be lowered in the second cycle as per site guidelines.

^b Dose in consolidation will be determined by the Sponsor after determination of all available data. It will not exceed induction dose.

^c On the basis of safety, tolerability, and clinical benefit and after consultation with the Medical Monitor, intra-patient escalation may be allowed to 200 mg.

^d On the basis of safety, tolerability, and clinical benefit and after consultation with the Medical Monitor, patient may be allowed to continue maintenance at the same dose within past the 12 cycles

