4.3.2.2 Cytarabine

Cytarabine will be administered in the first cycle of induction at a dose of 200 mg/m² QD by IV for 7 days, immediately after the corresponding dose of idasanutlin. Dose and regimen can be lowered per investigator choice in the second induction cycle

Cytarabine will be administered in consolidation at a dose of 1.5 g/m² QD for 5 days as IV infusion over a minimum of 3 hours, immediately after corresponding dose of idasanutlin.

The dose of cytarabine should be calculated based on a body weight measurement within 2 days of the first day of each cycle. To calculate body surface area (BSA) for the cytarabine dose, refer to [Appendix 9](#).

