Appendix 1: Schedule of Activities (cont.)

Table 2: Chemotherapy Consolidation

| Assessment/Procedure | Consolidation (28-Day Cycle) up to 4 Cycles | | | | | | | | |
|--|---|----|----|----|----|----|-----|-----|------------------|
| | D1 | D2 | D3 | D4 | D5 | D8 | D15 | D22 | D28 |
| Vital Signs ^a , weight, ECOG performance status | x | | | | | x | x | x | x ^b |
| Single 12-Lead ECG ^c | x | x | x | | x | | | | |
| Targeted physical examination ^d | x | | | | | x | x | x | x ^b |
| Urinalysis | x | | | | | | | | |
| Biochemistry ^e | x | x | | | x | x | x | x | x ^b |
| Hematology ^e | x | x | | | x | x | x | x | x ^b |
| FACIT-Fatigue, EORTC Item Library, PRO-CTCAE, EORTC QLQ-C30, EQ-5D-5L ^f | x | | | | | | | | |
| HMRA | | | | | | | | | x ^b |
| Bone marrow sampling for HMRA ^g | | | | | | | | | x ^b |
| Bone marrow sampling for MRD/Flow, EDTA, PAXgene [®] ^h | | | | | | | | | x ^b |
| Whole blood sampling for EDTA and clinical | x | | | | | | | | x ^{b,i} |
| RBR sampling, blood serum and plasma (optional) | x | | | | | | | | |
| PK sampling | Refer to Appendix 2 | | | | | | | | |
| Concomitant medications | To be recorded continually; see Section 4.4 | | | | | | | | |
| Adverse events | To be assessed continually; see Section 5.3.1 | | | | | | | | |
| Cytarabine (1.5 g/m ² IV) ^j | x | x | x | x | x | | | | |
| Idasanutlin (PO QD) ^j | x | x | x | x | x | | | | |

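### Section 3.1.3 gives the consolidation cytarabine dose in mg/m², while Table 4 and four other places give it in g/m²: a 1000-fold contradiction

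*Combined protocol and SAP*

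**What the plan says.** The protocol states the consolidation cytarabine dose for this trial in six places.

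- **Section 3.1.3, text on the expansion cohorts.** Patients in remission after up to two induction cycles are to receive "chemotherapy consolidation treatment up to 4 cycles with 1.5 mg/m² cytarabine", or an allogeneic transplant.
- **Section 3.1.3, Table 4 (expansion phase).** "Cytarabine 1.5 g/m² IV on Days 1–5 over 3 hr".
- **Section 3.1.2.2, Table 1 (dose-escalation phase).** "Cytarabine 1.5 g/m² IV on Days 1–5 administered over 3 hours".
- **Synopsis, Investigational Medicinal Products.** "Cytarabine will be administered in consolidation at a dose of 1.5 g/m² once a day (QD) for 5 days".
- **Section 4.3.2.2, Cytarabine.** "Cytarabine will be administered in consolidation at a dose of 1.5 g/m² QD for 5 days".
- **Appendix 1, Table 2 (chemotherapy consolidation).** The cytarabine row is labelled 1.5 g/m² IV, with administration marked on Days 1 to 5.

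Section 3.1.3 also says, just before the sentence in question, "All expansion patients will be enrolled and treated as described in" Table 4. Section 4.3.2, on dosage and administration, refers back to Section 3.1 for the regimens.

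**The concern.** The Section 3.1.3 sentence is an instruction about what expansion patients will receive, not background. It is also the only running text in Section 3.1 that gives a consolidation cytarabine dose: the corresponding dose-escalation text in Section 3.1.2.2 leaves the dose to Table 1. A reader sent from Section 4.3.2 to Section 3.1 therefore meets two values for the same drug in the same phase.

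The first stake is patient safety. Cytarabine is an investigational product here (Section 4.3) and is obtained locally (Sections 4.3.1.2 and 4.3.3), so sites prepare it from their own stock to the protocol's figure.

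The second is the trial's record. Section 5.4.4 defines overdose relative to the assigned dose, Section 5.4 puts overdoses and medication errors on the 24-hour reporting list, and Section 9.2 requires deviations to be documented. With two assigned doses in the text, any consolidation dose departs from one of them.

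The third is conditional. If a patient were misdosed, relapse, EFS, RFS, OS and safety in that expansion cohort would reflect a regimen other than the planned one.

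**Working it through.** No power, precision or error-rate formula applies. The check is a comparison of every statement of this dose, followed by a unit conversion.

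**Step 1. Statements side by side.**

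| Place | Dose as stated | In mg/m² |
|---|---|---|
| Section 3.1.3, text | 1.5 mg/m² | 1.5 |
| Section 3.1.3, Table 4 | 1.5 g/m² | 1,500 |
| Section 3.1.2.2, Table 1 | 1.5 g/m² | 1,500 |
| Synopsis | 1.5 g/m² | 1,500 |
| Section 4.3.2.2 | 1.5 g/m² | 1,500 |
| Appendix 1, Table 2 | 1.5 g/m² | 1,500 |

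One statement is in mg/m² and five are in g/m².

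**Step 2. Rule out other cytarabine figures as the explanation.** The 200 mg/m² figures are the induction dose. The 1 g/m² figures in Sections 1.2.2 and 3.3.1 describe other idasanutlin studies. Neither conflicts with the consolidation dose, and neither accounts for the difference.

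**Step 3. Size of the contradiction.** 1.5 g = 1.5 × 1,000 mg = 1,500 mg, and 1,500 / 1.5 = 1,000.

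**Step 4. Carry it through the schedule.** The Section 3.1.3 sentence gives a maximum of 4 cycles but no days. The 5 daily doses come from Table 4 and Section 4.3.2.2.

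- Per cycle: 5 × 1.5 = 7.5 mg/m², against 5 × 1,500 = 7,500 mg/m².
- Over 4 cycles: 4 × 7.5 = 30 mg/m², against 4 × 7,500 = 30,000 mg/m².

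**Step 5. Who is covered.** The expansion phase has about 40 patients (20 + 20). The sentence applies to those who reach remission and then have chemotherapy rather than transplant. The documents give no expected split, so 40 is an upper bound.

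**Step 6. What in the analysis depends on it.** The primary efficacy endpoint is CR at the end of induction (Section 6.3.1), assessed before consolidation starts. The intervals in Tables 14 and 15 and the mCRM work in Appendix 18 do not use this dose. EFS, RFS and OS (Section 6.3.2) and the safety summaries (Section 6.4) cover the consolidation period, but they would change only if a wrong dose were given.

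**The case against.** The best reply is that Table 4 governs. Section 3.1.3 says expansion patients are treated according to that table and cites it again straight after the disputed sentence. The sentence gives no route, days or infusion time, so nobody could prescribe from it alone. The consolidation schedule in Appendix 1 sends sites to Section 4.3.2, and the regimen table, the administration section and the schedule agree with one another. One statement standing against five, 1000-fold apart, is conspicuous and would probably be queried before any drug was given. It looks like a typographical slip, and nothing in the primary analysis turns on it.

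Much of this stands. It lowers the probability of harm, and it means that any effect on the secondary endpoints is conditional on a dosing deviation that has not been shown to be likely. It does not remove the contradiction. The protocol has no rule that a table overrides the text, and Section 4.3.2 refers readers to the part of the protocol that contains the sentence. That a pharmacist would probably notice is no substitute for a consistent dose for an investigational product.

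**Conclusion.** The concern holds. Section 3.1.3 contradicts its own Table 4 and the four other statements of the consolidation cytarabine dose by a factor of exactly 1000, in text that says what expansion patients will receive. No redaction, amendment note or precedence rule accounts for it.

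The reason to correct it before use is patient safety and an unambiguous assigned dose, not statistical validity. The conclusion assumes only that the unit in the sponsor's source file is the one seen in the PDF text. A text-extraction error cannot be wholly excluded, though the other five statements all read g/m², and a look at the source settles it.

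**What to change.** Reconcile the Section 3.1.3 text with Table 4, Table 1, Section 4.3.2.2, the synopsis and Appendix 1 Table 2, so that all six state the same dose in the same unit. Which statement is right is for the sponsor to confirm; this review does not choose. Having the Section 3.1.3 text refer to the regimen table without repeating the dose would remove one place where the two can diverge.

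The textual cost is very small. The procedural cost depends on Section 9.6, which requires IRB/EC approval (and regulatory approval where locally required) before a change is implemented, unless it removes an immediate hazard or is purely logistical or administrative. A formal amendment may therefore be needed, with sites told of the correction. No sample size, analysis or simulation has to be redone.

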3.1.4 Post-Treatment Follow-Up and Survival Follow-Up

Patients who complete treatment or discontinue treatment for reasons other than disease progression will undergo assessments (see [Appendix 1](#)) during the post-treatment follow-up period, which will continue until morphologic relapse or up to 2 years, whichever occurs first. Patients who experience morphologic relapse or were followed for 2 years in the post-treatment phase will be evaluated for survival status and

initiation of new anti-leukemia treatment until the end of the study. Details are provided in the schedules of activities (see [Appendix 1](#)).

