4.5.6 Tumor and Response Evaluations

Hematologic malignancy response will be assessed according to ELN and additional response criteria for AML (see [Appendix 19](#)).

Hematologic malignancy response assessments (HMRA) require sampling of blood and bone marrow on the same day as indicated (a window of 4 days is acceptable between the blood and bone marrow sampling). Bone marrow aspirates are required, but if bone marrow biopsies are performed, the biopsy results should be provided along with the aspirate. Depending on the timepoint in the schedule of activities, the HMRA is established on the basis of blood counts only, or includes the assessment of bone marrow. Patients will be considered to be in their best response state until definitive evidence of relapse is available from blood counts, bone marrow aspirate, or bone marrow biopsy.

In the event that a bone marrow aspirate or biopsy is equivocal (i.e., a recovering marrow), the bone marrow assessment and complete blood count should be repeated > 7 days later.

In case disease progression/relapse is determined solely by symptomatic deterioration or by a hematology assessment, a bone marrow aspirate should be performed at that time to complete HMRA. If a patient progresses or relapses outside of the scheduled visit, an unscheduled HMRA must be provided.

If a bone marrow aspirate is performed at any unscheduled timepoint during the study, an unscheduled HMRA must be provided.

Please note that at the time of bone marrow sampling for HMRA, the bone marrow sample collected (aspirate) should also allow for further analyses (e.g., MRD by flow cytometry, MRD by NGS) and the amount taken should be taken into consideration.

During the treatment period, HMRA are to be performed and reviewed before the start of a new treatment cycle. In the event that a patient has a dosing delay > 7 days in consolidation or induction, weekly blood counts must be performed for HMRA to

document evidence of non-progression. Treatment failure and relapse will lead to discontinuation of the study medication and patients will enter follow-up (see [Appendix 1](#)).

During the follow-up of patients who remain in remission after treatment, blood will be required every month and a bone marrow aspirate will be required every 6 months to allow for HMRA until relapse. Refer to [Appendix 1](#) for further details.

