Appendix 1: Schedule of Activities (cont.)

Table 5: Post-Treatment Phase (cont.)

CTCAE=Common Terminology Criteria for Adverse Events; eCRF=electronic Case Report Form; EDTA=ethylenediaminetetraacetic acid; EORTC=European Organisation for Research and Treatment of Cancer; EORTC QLQ-C30=EORTC Quality-of-Life Questionnaire–Core 30; EQ-5D-5L=EuroQol 5-Dimension, 5-Level; FACIT=Functional Assessment of Chronic Illness Therapy; HMRA=hematologic malignancy response assessment; MRD=minimal residual disease; PRO=patient-reported outcome; PRO-CTCAE=Patient-Reported Outcomes Common Terminology Criteria for Adverse Events; Q1M=once a month; Q3M=once every 3 months; Q6M=once every 6 months; Tx=treatment.

- ^a Patients who discontinue treatment for any reasons other than morphological relapse (see Section 4.5.6) will undergo assessments during the post-treatment follow-up period, which will continue until morphological relapse (see Section 4.5.6) or 2 years, whichever occurs first. The first post-treatment follow-up visit is 1 month after the end of drug discontinuation visit.
- ^b Patients who experience morphological relapse (see Section 4.5.6) or ended their 2 years post-treatment follow-up will be evaluated for survival status and new anti-leukemia treatment every 3 months during the survival follow-up period, which will continue until the end of the study.
- ^c For HMRAs during the study, bone marrow aspirates are required, but bone marrow biopsies may be performed at the discretion of the investigator.
- ^d Bone marrow MRD/Flow, EDTA, and PAXgene to be collected at same time as bone marrow for response assessment. If unscheduled bone marrow aspirate is being collected for hematologic response assessment, then bone marrow MRD/Flow, EDTA, and PAXgene samples should also be collected. If any MRD assessments are done locally, please record this information in the eCRF. The priorities are MRD/FLOW > EDTA > PAXgene.
- ^e PRO questionnaires need to be self-administered before the patient receives any information on disease status. Completion of PROs should occur prior to the performance of non-PRO assessments whenever possible. PRO assessments include the FACIT-Fatigue, EORTC QLQ-C30, EORTC Item Library symptoms, PRO-CTCAE, and EQ-5D-5L.

Appendix 2

Schedule of Pharmacokinetic and PD Biomarker Samples

Table 1 All Cohorts

| Study Visit | | Plasma Idasanutlin PK Sample | Serum MIC-1 Sample | Plasma Cytarabine PK Sample | Plasma Daunorubicin PK Sample |

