Appendix 19: Response Criteria for Acute Myeloid Leukemia (cont.)

Table 1 Response Criteria for Acute Myeloid Leukemia

| Response | Definition |
|--------------------------------|---|
| CR | Bone marrow blasts <5%; absence of circulating blasts and blasts with Auer rods; absence of extramedullary disease; ANC $\geq 1.0 \times 10^9/L$ (1000/ μ L); and platelet count $\geq 100 \times 10^9/L$ (100,000/ μ L) |
| CRi | All CR criteria except for residual neutropenia (ANC < $1.0 \times 10^9/L$ [1000/ μ L]) or residual thrombocytopenia (platelet count < $100 \times 10^9/L$ [100,000/ μ L]) |
| CRp | All CR criteria except for residual thrombocytopenia (platelet count < $100 \times 10^9/L$ [100,000/ μ L]) |
| CRh | All CR criteria except ANC > $0.5 \times 10^9/L$ (500/ μ L) but < $1.0 \times 10^9/L$ (1000/ μ L) and platelet count > $50 \times 10^9/L$ (50,000/ μ L) but < $100 \times 10^9/L$ (100,000/ μ L) |
| MLFS | Bone marrow blasts <5%; absence of blasts with Auer rods; absence of extramedullary disease; and residual neutropenia (ANC < $0.5 \times 10^9/L$ [500/ μ L]) and residual thrombocytopenia (platelet count < $50 \times 10^9/L$ [50,000/ μ L]) |
| PR | All hematologic criteria for CR; bone marrow blast percentage of 5%-25%; and $\geq 50\%$ decrease from baseline in percentage of bone marrow blasts |
| SD | Absence of CR, CRi, CRp, CRh, MLFS, and PR; and no clinical or cytologic progressive disease by investigator assessment |
| PD | Evidence of an increase in bone marrow blast percentage and/or increase in absolute blast counts in the blood, defined as at least one of the following: 
 • >50% increase from baseline in bone marrow blasts (a minimum increase of 15 percentage points is required in cases with <30% bone marrow blasts at baseline) • >50% increase in peripheral blasts (WBC count \times % blasts) to $> 25 \times 10^9/L$ (25,000/μL) (in the absence of differentiation syndrome) • New extramedullary disease |
| Hematologic relapse | Following CR, CRi, CRp, or CRh, development of extramedullary disease or reappearance of either of the following that is not attributable to another cause (e.g., bone marrow regeneration after consolidation therapy): peripheral blasts or $\geq 5\%$ bone marrow blasts |
| Death in aplasia | Death occurring ≥ 7 days following completion of induction treatment while cytopenic, with an aplastic or hypoplastic bone marrow obtained within 7 days of death and no evidence of persistent leukemia |

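### Section 3.1.4 and Appendix 1 give conflicting entry rules for post-treatment follow-up; under Section 3.1.4 as worded, a patient who progresses without ever remitting enters no follow-up period, so OS may be overstated where sites apply it

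*Combined protocol and SAP*

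**What the plan says.** **Entry to post-treatment follow-up (monthly blood, 6-monthly marrow)**
- Section 3.1.4: "Patients who complete treatment or discontinue treatment for reasons other than disease progression will undergo assessments".
- Appendix 1, Table 5, footnote a: "Patients who discontinue treatment for any reasons other than morphological relapse (see Section 4.5.6) will undergo assessments during the post-treatment follow-up period".

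**Entry to survival follow-up**
- Section 3.1.4: "Patients who experience morphologic relapse or were followed for 2 years in the post-treatment phase will be evaluated for survival status".
- Footnote b: "Patients who experience morphological relapse (see Section 4.5.6) or ended their 2 years post-treatment follow-up will be evaluated for survival status", with contact every 3 months to the end of the study. These two rules agree.

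**Section 4.5.6** says "Treatment failure and relapse will lead to discontinuation of the study medication and patients will enter follow-up". It names no period and points to Appendix 1. It also sets the sampling frequency for one group: "During the follow-up of patients who remain in remission after treatment, blood will be required every month and a bone marrow aspirate" is due every 6 months.

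**Definition of relapse.** Footnotes a and b refer to Section 4.5.6 for morphological relapse, but that section does not define it. Appendix 19 defines only hematologic relapse, which begins "Following CR, CRi, CRp, or CRh, development of extramedullary disease or reappearance". It lists progressive disease as a separate category.

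**OS** is a secondary endpoint, analyzed descriptively by Kaplan-Meier with landmarks from 6 months to 2 years and censored at the date last known alive (Section 6.3.2).

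**The concern.** The two rules for post-treatment follow-up exclude different patients. The difference falls on one group: those who stop during induction with progressive disease and have never been in remission. Section 3.1.4 excludes them from post-treatment follow-up because they stopped for progression. They cannot enter survival follow-up by relapsing, because relapse as Appendix 19 defines it needs a remission first. They cannot enter it by completing 2 years of a period they never joined.

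OS is the endpoint at stake. EFS already counts treatment failure as an event, and RFS is measured only in patients who remit. A patient with no scheduled contact after the discontinuation visit, 28 days after the last dose, would be censored in the OS analysis at about that date. Such patients are likely to have a worse prognosis than the rest of the cohort, so the censoring would be informative. If their later deaths also went unrecorded, the Kaplan-Meier curve would lie too high. Survival contacts that were never scheduled may be hard to recover later.

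**Working it through.** **Step 1. Follow each type of patient through the two texts.** Relapse is taken in the Appendix 19 sense.

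| Patient who stops treatment | Section 3.1.4 | Table 5, footnotes a and b |
|---|---|---|
| In remission, treatment completed or stopped for toxicity | Post-treatment, then survival | Post-treatment, then survival |
| Relapse after remission | Survival | Survival |
| Never remitted, stable disease or partial remission | Post-treatment, then survival | Post-treatment, then survival |
| Toxicity before remission or declared failure | Post-treatment, then survival | Post-treatment, then survival |
| Never remitted, progressive disease | **Neither** | Post-treatment, then survival |

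Only the last row differs.

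**Step 2. Check whether other text settles that row.**
- Section 4.6.1 sends everyone who stops study medication to Appendix 1, and Sections 3.1.4 and 4.5.6 also refer to it. This favors footnote a, but no sentence says which text prevails where they differ.
- Section 3.1.2.2 has all patients followed for progression and survival. That is dose-escalation text. Section 3.1.3, which covers the expansion phase and so the high-risk cohort, has no such sentence.
- Section 5.6 asks for all deaths after the adverse event period to be reported, but sets no contact schedule.
- Section 3.2 sets how long follow-up lasts, not who is contacted or how often.
- Table 5 marks the survival follow-up row only in the survival column, and footnote b gives treatment failure or progression no direct entry.

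**Step 3. Illustrate the size if such patients were lost.** The plan states no figure to reproduce. Assumptions that are not in the documents:
- share of the cohort with PD, f = 5% to 25%;
- 12-month OS of 10% to 30% with PD and 60% to 70% otherwise, with exponential survival in each group;
- every PD patient censored at month c = 2 or 3, with later deaths unrecorded.

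Let h_P and h_O be the monthly hazards with and without PD.
- True survival: S(t) = f·exp(−h_P·t) + (1−f)·exp(−h_O·t)
- Large-sample Kaplan-Meier value for t > c: S(c)·exp(−h_O·(t−c))

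Example with f = 0.10, 12-month OS of 20% and 60%, c = 2:
- h_P = −ln(0.20)/12 = 0.1341 and h_O = −ln(0.60)/12 = 0.0426
- True S(12) = 0.10 × 0.20 + 0.90 × 0.60 = 0.560
- S(2) = 0.10 × 0.765 + 0.90 × 0.918 = 0.903
- Kaplan-Meier at 12 months = 0.903 × exp(−10 × 0.0426) = 0.903 × 0.653 = 0.590
- Overstatement = 0.590 − 0.560 = 3.0 points

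Over the whole grid:

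| PD share | Overstatement at 12 months | Overstatement at 24 months |
|---|---|---|
| 5% | 1.0 to 2.0 points | 1.1 to 1.8 points |
| 10% | 2.0 to 4.1 points | 2.1 to 3.6 points |
| 20% | 4.1 to 8.1 points | 4.3 to 7.2 points |
| 25% | 5.1 to 10.2 points | 5.3 to 8.9 points |

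For scale, the binomial standard error at N = 20 and S = 0.56 is √(0.56 × 0.44 / 20) = 0.111, or 11 points.

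**The case against.** The strongest reply is that the gap exists only if Section 3.1.4 is read alone. That section refers to Appendix 1 for details, as do Sections 4.5.6 and 4.6.1, and footnote a there covers the never-remitted patient with monthly contact, which is more frequent than the 3-monthly survival contact. Section 5.6 then requires deaths of any cause to be reported. Disease progression in Section 3.1.4 may also be loose wording for relapse, since Section 4.5.6 pairs the two terms. Most of this stands. It shows that survival follow-up was intended and that a site working from Appendix 1 would do it. It does not remove the conflict: the body text excludes a group that the appendix includes, and the relapse term used in both places is not defined.

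Four stronger readings are tempting, and the documents do not support them.
- *A reader might infer that the plan as a whole misses these deaths and so overstates OS.* It does not; this follows only where Section 3.1.4 is applied in preference to Appendix 1.
- *A reader might count Section 4.5.6 as a third entry rule.* It gives a sampling frequency for patients in remission and leaves entry to Appendix 1.
- *A reader might take all patients without CR as affected,* about 9 to 10 of 20 at the high-risk benchmark of 50% to 55%. That count includes CRi, CRp, CRh, MLFS, stable disease, partial remission and early death. Only PD without prior remission is concerned.
- *A reader might say that marrow samples from refractory patients under footnote a serve no purpose.* They add nothing to that patient's EFS or RFS, but Sections 2.4 and 4.5.8.3 list resistance among the biomarker aims.

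**Conclusion.** The inconsistency is real and specific. Section 3.1.4 and footnote a conflict on who enters post-treatment follow-up, and on the wording of Section 3.1.4 a patient with PD who never remitted has no follow-up period. Upward bias in OS is a conditional risk: a site must apply Section 3.1.4, and the later deaths must go unrecorded despite Section 5.6.

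The size cannot be determined from the documents, which give neither the PD share nor survival after progression. Under the assumptions shown, the overstatement at 12 months is about 2 to 4 points if 10% of a cohort has PD, which is 2 of 20 patients. That is well inside the 11-point standard error. It is a worst case, because it assumes that every such patient is lost. OS is descriptive and untested, so no error rate, power or sample size is affected. The correction is worth making because it removes an avoidable source of informative censoring at little cost.

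**What to change.** - Reconcile Section 3.1.4, Section 4.5.6 and Table 5 footnotes a and b to one entry rule, and replace morphologic relapse with the term defined in Appendix 19.
- State that survival status is collected at least every 3 months for every treated patient, whatever the reason for stopping, until death, withdrawal of consent or end of study. Name treatment failure, PD and toxicity before remission explicitly. A rule that names only remission on one side and failure, progression or relapse on the other would leave out patients who stop for toxicity before either is declared.
- Add treatment failure or PD to footnote b as a direct entry to survival follow-up.
- The sponsor should reconcile which off-treatment patients have the monthly blood and 6-monthly marrow assessments.

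The cost is wording in two sections and two footnotes, plus a few extra survival contacts. With survival status collected for every treated patient, the bias from this source disappears.
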